### Study design

This was a non-randomized, pre- and post-intervention trial. Since the intervention program started in May 2015, the period from January 2013 to December 2014 was defined as the pre-intervention period, and the period from January 2015 to December 2016 was defined as the post-intervention period. The TM cases were defined as the cases for which an TM alert was sent. Other cases were defined as standard care cases (non-TM cases).

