#### Data collection and variables

We collected data from the Korean OHCA Registry including the ambulance run sheet, dispatch record, cardiac arrest in-depth registry, and medical records for outcomes from the Korea Centers for Disease Control and Prevention. We developed the TM alert system registry by linking the TM cases that had a message sent to the registered volunteers. We checked the OHCA registry to confirm whether or not the case was a real arrest. Such cases were excluded if they were not a cardiac arrest or death was confirmed at the scene and no transfer to the emergency department (ED) occurred.

The main exposure of interest was the intervention phase (before- and after-intervention periods), and the secondary exposure was TM sent from the TM alert system. Demographic factors that were collected included the following: date of arrest, time of the call (00:01-05:59, 06:00-11:59, 12:00-17:59, and 18:00-23:59), age, gender, and comorbidities (diabetes, hypertension, heart disease, and stroke). Community and EMS factors that were collected included the following: witness information, location of the arrest, bystander CPR, laypersons' use of a PAD, primary electrocardiogram (ECG) at the scene, EMS response time interval (RTI, from the time of the call to the time of EMS arrival at the scene), scene time interval (STI, from the time of arrival at the scene to the time of departure from the scene), transport time interval (TTI, from the time of departure from the scene to the time of EMS arrival at the hospital), prehospital airway management by an EMS provider (endotracheal intubation, supraglottic airway device, or bag valve mask). Hospital factors included the emergency department (ED) level (regional level 1 ED, local level 2 ED, local level 3 ED) and post-resuscitation care, such as percutaneous coronary intervention (PCI), targeted temperature management (TTM), and extracorporeal membrane oxygenation (ECMO).

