#### Main outcomes

The primary endpoint was good neurological outcomes of OHCA patients, which were classified as

cerebral performance category I or II at discharge. The secondary endpoints were the survival to discharge and prehospital ROSC. The tertiary outcomes were the provision of bystander CPR, regardless of dispatcher-provided CPR instructions, and bystander defibrillation.

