### Statistical analysis

The demographics of the registered volunteers, registered PADs, and the number of TM alerts sent during the study period were compared for the study setting. A descriptive analysis was performed to determine the distribution of the categorical variables (counts and proportions) and continuous variables (medians and inter-quartile ranges). The chi-square test was performed for categorical variables, and the Wilcoxon rank-sum test was performed to compare continuous variables across the intervention periods.

Adjusted odds ratios (ORs) with 95% confidence intervals (CIs) for bystander CPR and defibrillation by TM versus non-TM were calculated using multivariable logistic regression analysis with adjustment for potential confounders. Adjustment for age, gender, and comorbidities were included as confounders in Model 1, and time factors (season, weekend, and time of the arrest) and characteristics of the arrest (witnessed, location of arrest) in addition to the confounders in Model 1 were added in Model 2.

Multivariable logistic regression analyses for outcomes (good CPC, survival to discharge, and PROSC) were used. Model 1 was adjusted for demographic factors (age, gender, and comorbidities); Model 2 was adjusted for the demographic factors from Model 1 as well as time factors related to the event (season, weekday, and daytime), Utstein factors (initial ECG, witness, and place), and EMS factors (RTI, STI, TTI, and prehospital airway); Model 3 was adjusted for the same confounders as Models 1 and 2 as well as factors related to advanced hospital care (PCI, TTM, and ECMO).

For the sensitivity analysis, a final multivariable logistic regression analysis was conducted for the subgroup population when the call occurred during the study time (TM sent time), from 6 AM to 10 PM. The confounders were same as the main analyses for each outcome. The main exposure was TM (cases who received TM alerts) versus non-TM (cases who did not receive TM alerts) for bystander CPR and defibrillation during the before- and after-intervention periods for outcomes (PROSC, survival to discharge, and good CPC).

All the statistical analyses were conducted using SAS software, version 9.4 (SAS Institute Inc., Cary, NC, USA). P values were based on a two-sided significance level of 0.05.

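### EMS response time is collected and adjusted for in the fuller clinical-outcome models, but is in neither bystander CPR/defibrillation model; a residual difference by alert status could mimic or mask an alert effect

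*Combined protocol and SAP*

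**What the plan says.** All references are to the combined protocol and SAP.

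- **Bystander models (Statistical analysis).** Odds ratios for "bystander CPR and defibrillation by TM versus non-TM were calculated using multivariable logistic regression analysis with adjustment for potential confounders". On the first set: "Adjustment for age, gender, and comorbidities were included as confounders in Model 1". Model 2 adds "time factors (season, weekend, and time of the arrest) and characteristics of the arrest (witnessed, location of arrest"). There is no third bystander model, and RTI is in neither of the two.
- **Clinical-outcome models (same section).** For good CPC, survival to discharge and prehospital ROSC, Model 2 includes "EMS factors (RTI, STI, TTI, and prehospital airway"). Model 3 carries these forward. Clinical Model 1 is demographic only and has no RTI.
- **Availability (Data collection and variables).** The registry variables include the "EMS response time interval (RTI, from the time of the call to the time of EMS arrival at the scene").
- **Sensitivity analysis (Statistical analysis).** For calls between 6 AM and 10 PM: "The confounders were same as the main analyses for each outcome". RTI is therefore absent there too for bystander outcomes.
- **Comparator (Study design).** After defining TM cases as those with an alert sent: "Other cases were defined as standard care cases (non-TM cases").
- **Rank (Main outcomes).** "The tertiary outcomes were the provision of bystander CPR, regardless of dispatcher-provided CPR instructions, and bystander defibrillation".

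No reason is given for using RTI in one family of models and not in the other.

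**The concern.** A bystander can mostly act only until the ambulance crew arrives, so RTI approximates the time available for both bystander outcomes. A text sent to volunteers should not alter the ambulance's arrival, so RTI is not an obvious mediator of the alert. It is a reasonable adjustment variable, and arguably matters more directly here than in the clinical models that do include it.

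TM versus non-TM is not a randomised contrast. Non-TM covers every case without an alert: all arrests before the programme began, night arrests, and arrests the dispatcher did not recognise. If RTI differs between the groups after Model 2 adjustment, part of the estimated odds ratio reflects time available rather than the alert. A longer RTI in TM cases would inflate the apparent effect, and a shorter one would hide a real effect.

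The planned covariates may capture some of such a difference, but not clearly all of it:

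- The bystander models contain no calendar year or period, so season, weekend and time of day cannot absorb a drift in RTI between 2013 and 2016.
- Call time is collected in six-hour bands, and the 18:00-23:59 band straddles the 22:00 end of alerting. If those bands are what enters the model, eligible and ineligible hours are mixed.
- Continuous variables are to be compared across intervention periods, not by TM status, so a reader could not see whether RTI differs on the contrast that matters.

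**Working it through.** **Step 1: covariate lists side by side.**

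| Model | Covariates | RTI? |
|---|---|---|
| Bystander 1 | age, gender, comorbidities | no |
| Bystander 2 | Bystander 1 + season, weekend, time of arrest, witnessed, location | no |
| Clinical 1 | age, gender, comorbidities | no |
| Clinical 2 | Clinical 1 + season, weekday, daytime, initial ECG, witness, place, RTI, STI, TTI, airway | yes |
| Clinical 3 | Clinical 2 + PCI, TTM, ECMO | yes |

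The omission is a matter of text and needs no assumption.

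**Step 2: size.** The documents give no RTI distribution, no RTI by TM status, no RTI-bystander association, no bystander rates and no case numbers. There is no stated figure to reproduce, and every input below is an assumption. Shift means the TM minus non-TM difference in mean RTI left after Model 2, with no true alert effect.

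*(a) Log-linear association.* Spurious OR ≈ (OR per minute)^shift.

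| OR per minute | +0.5 min | +1 min | -0.5 min | Shift needed for OR 1.2 |
|---|---|---|---|---|
| 1.02 | 1.01 | 1.02 | 0.99 | 9.2 min |
| 1.05 | 1.02 | 1.05 | 0.98 | 3.7 min |
| 1.10 | 1.05 | 1.10 | 0.95 | 1.9 min |
| 1.20 | 1.10 | 1.20 | 0.91 | 1.0 min |

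The last column is ln(1.2)/ln(OR per minute).

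*(b) Constant hazard from the call.* p = 1 - exp(-h × RTI), so the odds are exp(h × RTI) - 1. The reference RTI is 6 minutes.

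- h = 0.05, 6.5 v 6 min: (e^0.325 - 1)/(e^0.30 - 1) = 0.384/0.350 = 1.10.
- h = 0.12, 6.5 v 6 min: (e^0.78 - 1)/(e^0.72 - 1) = 1.181/1.054 = 1.12.
- 7 v 6 min: 1.20 at h = 0.05 and 1.25 at h = 0.12.

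*(c) Window model with a start-up delay.* p = mean of 1 - exp(-h × max(RTI - delay, 0)). RTI is gamma with mean 7 and SD 2.5 minutes, and h is solved to match an assumed base rate.

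| Scenario | +0.5 min | +1 min | -0.5 min |
|---|---|---|---|
| CPR, base rate 40-60%, delay 0-3 min | 1.10-1.24 | 1.20-1.52 | 0.80-0.91 |
| CPR, base rate 40-60%, 80% of CPR immediate, delay 3 min for the rest | 1.04-1.06 | 1.08-1.12 | 0.95-0.96 |
| Defibrillation, base rate 0.5-3%, fetch delay 2-6 min | 1.10-1.22 | 1.20-1.48 | 0.81-0.90 |

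Across (a) to (c), +0.5 minute gives about 1.01 to 1.24 and -0.5 minute about 0.80 to 0.99.

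**Step 3: effect on the test.** Two-sided 0.05 Wald test with 600 TM and 3,000 non-TM cases (assumed). SE = √[1/(n₁p₁(1-p₁)) + 1/(n₀p₀(1-p₀))] and z = ln(OR)/SE.

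Example: p₀ = 0.60, spurious OR 1.10. Odds 1.5 × 1.10 = 1.65, so p₁ = 0.623. SE = √(0.00709 + 0.00139) = 0.092 and z = 0.0953/0.092 = 1.03. The rejection rate is about 18% against a nominal 5%.

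| Spurious OR | Bystander CPR at 60% | Defibrillation at 1% |
|---|---|---|
| 1.05 | 8% | 5% |
| 1.10 | 18% | 6% |
| 1.20 | 50% | 7% |

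**The case against.** The strongest reply is that confounding needs two facts the documents do not supply: an RTI difference by TM status that survives adjustment, and a material RTI-bystander association. This stands. A reader might infer that a small RTI shift does produce an apparent alert effect, or that the bystander results are biased upwards. The documents support neither inference. Direction is unknown, and the bias may be negligible.

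The size also depends on the model. A constant hazard from call to arrival makes RTI the whole time at risk. The Study setting section says dispatcher-assisted CPR has been in place since late 2010, and the outcome counts bystander CPR whether or not the dispatcher instructed it. CPR begun before or during the call depends little on ambulance arrival. If most CPR starts at once, the spurious odds ratio for +0.5 minute falls to 1.04-1.06. This stands too, so the narrow 1.10-1.12 from the constant-hazard model should not be quoted alone.

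Three further points limit the concern. The daytime analysis removes night cases, although pre-programme and unrecognised arrests remain in the comparator. Rejection rates for rare defibrillation barely move. RTI runs from the call, whereas the alert follows the dispatcher's two questions, so RTI only approximates the alerted volunteer's window.

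Finally, a different outcome may properly have a different covariate set. That is true in general, but it does not explain leaving out a collected variable that bounds the outcome itself, and the plan offers no explanation.

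**Conclusion.** The point holds in a limited form. RTI is collected and used in clinical Models 2 and 3, but it is missing without explanation from both bystander models, in the main and the daytime analysis. A residual RTI difference between TM and non-TM cases could mimic or mask an alert effect on bystander CPR and defibrillation.

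Neither size nor direction can be derived from the documents. The ranges in the working rest wholly on assumed RTI distributions, base rates, delays and associations. They show that the bias could be trivial or could matter, not that it is present.

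The consequence is small. The affected outcomes are tertiary and TM is the secondary exposure. A reader might extend the concern to the primary endpoint, but Models 2 and 3 for good neurological outcome already include RTI. This is a low-priority improvement.

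**What to change.** - Add RTI as a continuous term (spline or log) to Model 2 for bystander CPR and bystander defibrillation, in both the main and the 6 AM to 10 PM analyses. Show the estimates with and without it.
- Leave STI, TTI and prehospital airway out of these models. They follow EMS arrival, and so come after the bystander's opportunity.
- Report the RTI distribution by TM status alongside the planned comparison by period.
- If RTI is still to be left out, state the reason.

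The cost is one covariate already in the registry and one table row. Two limits should be stated with the result. RTI starts at the call rather than the alert, so adjustment is approximate. It also does not remove secular trend or selection by dispatcher recognition from the non-TM comparator, which need separate handling.

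### As written, Model 3 adjusts prehospital ROSC for hospital care given after it; for good CPC and survival Model 3 is not a total effect, and no model is named as the main result

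*Combined protocol and SAP*

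**What the plan says.** Data collection and variables defines the exposure: "The main exposure of interest was the intervention phase (before- and after-intervention periods"). Whether a text message was sent is the secondary exposure. The same section lists, among hospital factors, "post-resuscitation care, such as percutaneous coronary intervention (PCI), targeted temperature management (TTM), and extracorporeal membrane oxygenation (ECMO").

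Main outcomes makes good CPC at discharge primary and adds: "The secondary endpoints were the survival to discharge and prehospital ROSC".

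Statistical analysis then treats the three patient outcomes together: "Multivariable logistic regression analyses for outcomes (good CPC, survival to discharge, and PROSC) were used". The covariate sets are:

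- Model 1: "Model 1 was adjusted for demographic factors (age, gender, and comorbidities").
- Model 2: Model 1 plus season, weekday and daytime, and "Utstein factors (initial ECG, witness, and place), and EMS factors (RTI, STI, TTI, and prehospital airway").
- Model 3: "Model 3 was adjusted for the same confounders as Models 1 and 2 as well as factors related to advanced hospital care", namely PCI, TTM and ECMO.

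The 6 AM to 10 PM sensitivity analysis reuses these sets. Bystander CPR and defibrillation have a separate Model 2 with demographics and time factors, in which "characteristics of the arrest (witnessed, location of arrest) in addition to the confounders in Model 1 were added in Model 2". No model is named as the main one for any outcome.

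**The concern.** A confounder must not be a consequence of the outcome. PROSC has occurred, or failed to occur, before the patient reaches hospital. Patients with PROSC are more likely to live long enough to be offered PCI, TTM or ECMO, so Model 3 for PROSC conditions on something that PROSC partly determines. If the use of that care differs by period, the adjustment creates an association between period and PROSC where none exists.

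For good CPC and survival, hospital care comes before the outcome, so the timing error does not arise. But care depends on early resuscitation success, which the programme is meant to improve. Model 3 may therefore remove part of the effect, and it is not in general the total programme effect. With three odds ratios for the primary endpoint and none named as the main result, a reader cannot tell which one answers the trial's question.

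**Working it through.** The plan gives no event rates, care rates or effect sizes, so there is no figure of its own to reproduce. The structural part rests on the text; the sizes below rest on assumed rates.

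**Order of events.** The alert goes out during the emergency call. Scene care and PROSC (or its absence) follow, then transport, then hospital care, then discharge status. PCI, TTM and ECMO lie after PROSC and before good CPC and survival.

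**Mechanism for PROSC, checkable by hand.** Assume one care item and no programme effect: PROSC is 11% in both periods, and 90% of patients with PROSC and 18% of those without are admitted. Care is given to 10% of admitted patients before.

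1. Let the odds of care rise 1.5-fold: 0.10/0.90 = 0.1111; × 1.5 = 0.1667; probability 0.1667/1.1667 = 0.1429.
2. Share receiving care with PROSC: 0.90 × 0.10 = 0.0900 before, 0.90 × 0.1429 = 0.1286 after. Without PROSC: 0.18 × 0.10 = 0.0180 before, 0.18 × 0.1429 = 0.0257 after.
3. Among patients without care, the odds of PROSC are (0.11/0.89) × (1 − share with PROSC)/(1 − share without PROSC). The last factor is 0.9100/0.9820 = 0.9267 before and 0.8714/0.9743 = 0.8944 after. Period OR = 0.8944/0.9267 = 0.965.
4. Among patients with care the factor is 0.0900/0.0180 = 5 before and 0.1286/0.0257 = 5 after. Period OR = 1.00.

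The unadjusted OR is exactly 1.00. The care-adjusted OR lies between 0.965 and 1.00, near 0.965 because most patients receive no care. If care is stable, steps 3 and 4 both give 1.00. Three care items enlarge the shift.

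**Full illustration.** Expected cell counts (2,048 cells, so no simulation error) follow the chain: period, witnessed (55%), public place (20%) and unmeasured severity, then shockable rhythm (22%), PROSC, admission, the three care items and good CPC. The grid has 54 baselines:

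- PROSC 5, 11 or 20%, with good CPC half of that
- admission 75 or 90% with PROSC, and 10, 18 or 25% without
- PCI/TTM/ECMO among admitted 5/5/1, 10/10/2 or 20/25/4%

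Model 3 here is period, witnessed, place, ECG and the three care items. STI, TTI and airway are left out to isolate the care terms, so it is a reduced form of the plan's Model 3.

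PROSC, true OR 1.00:

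| Care odds, after vs before | Without care terms | Model 3 |
|---|---|---|
| 0.8 | 1.00 | 1.01-1.07 |
| 1.0 | 1.00 | 1.00 |
| 1.2 | 1.00 | 0.94-0.99 |
| 1.5 | 1.00 | 0.87-0.97 |
| 2.0 | 1.00 | 0.77-0.95 |

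Good CPC, no programme effect:

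| OR of each care item on CPC | Care odds | Without care terms | Model 3 |
|---|---|---|---|
| 1 | 1.5 | 1.00 | 0.85-0.96 |
| 1 | 2.0 | 1.00 | 0.74-0.92 |
| 2 | 1.5 | 1.02-1.10 | 0.86-0.96 |
| 2 | 2.0 | 1.03-1.18 | 0.76-0.92 |
| 4 | 1.5 | 1.03-1.20 | 0.86-0.96 |
| 4 | 2.0 | 1.05-1.37 | 0.76-0.92 |

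If the odds of care fall to 0.8 and each item has OR 2, the directions reverse: 0.95-0.99 without care terms, 1.02-1.08 in Model 3. With stable care both give 1.00.

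With a working programme (OR 1.25 on PROSC) and care that does not affect CPC, the model without care terms gives a CPC OR of 1.12-1.18. Model 3 gives 1.12-1.18 if care is stable, 0.97-1.12 if its odds rise 1.5-fold and 1.15-1.26 if they fall to 0.8.

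**These ranges are not bounds.** A separate simulation with other assumed coefficients, no true effect and care log OR 0.5 (about 1.65-fold) gave a Model 3 PROSC OR of 0.78. That is close to the grid's lowest value for a doubling.

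**Covariate sets.** For patient outcomes, Model 1 lacks witness, place and time. Model 2 adds them only together with ECG, RTI, STI, TTI and airway. Shifting the odds of witnessed arrest by 0.8 or 1.25, with no programme effect, moves a model that omits it only to 0.96-0.97 or 1.03-1.04 for CPC.

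**The case against.** The best defence of Model 3 is that the exposure is calendar period and the comparison has no concurrent control. Hospital care may then be a secular co-intervention as well as a consequence of resuscitation, and adjusting for it asks a legitimate question. For good CPC and survival this stands. The second table shows that leaving care out can produce a false benefit when care improves outcome and its use rises. It is a reason to keep Model 3 as a labelled supplement, but it does not help for PROSC, which care cannot affect.

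It can also be said that Model 3 was meant only for good CPC and survival. That may be so, but the text does not say it. Models 1 and 2 already give PROSC estimates free of hospital care, which limits the damage.

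Three stronger readings are tempting:

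- A reader might infer that Model 3 always works against the programme, or that the trial's result is off by a known amount. The documents give no care rates by period, so neither follows.
- A reader might infer that a model without hospital care gives the unbiased programme effect. With period as the exposure it does not; the trend in care remains in it.
- A reader might infer that Model 2 is invalid because STI, TTI and airway arise after the alert. No harm from them has been shown. Initial ECG may be a mediator or a case-mix marker, and the documents cannot settle which. The missing covariate set is therefore a minor point.

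**Conclusion.** The PROSC part is wrong as written. A prehospital outcome is adjusted for later hospital treatment, and the estimate is biased whenever care use differs by period. On the assumed rates the null OR becomes 0.87-0.97 for a 1.5-fold rise in the odds of care and 0.77-0.95 for a doubling, against 1.00 without the care terms. If care use was stable there is almost no distortion.

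For good CPC and survival the finding is narrower. Model 3 is not in general a total programme effect, but neither type of model is safe if care changed. With no programme effect and a doubling of care odds, Model 3 for CPC falls to 0.76-0.92, while models without care terms rise to about 1.18 (OR 2 per item) or about 1.37 (OR 4). The plan needs a named main model and a plain statement of this limit. It should be fixed; it does not by itself invalidate the trial.

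**What to change.** 1. Remove PCI, TTM and ECMO from every PROSC model, including the 6 AM to 10 PM analysis.
2. For good CPC and survival, name one model without hospital care as the main result and give the reason. The plan is written in the past tense; if results exist, declare the choice post hoc. Keep Model 3, labelled as supplementary and not a total effect. Show PCI, TTM and ECMO use by period beside both; the plan already compares categorical variables across periods. State that if care rose, the main model may overstate and Model 3 may understate the programme effect.
3. Minor: for each patient outcome, add the covariate set already used in the bystander Model 2 (demographics, time factors, witnessed, location), without RTI, STI, TTI or airway. Show it with and without initial ECG. RTI stays out because it ends at EMS arrival, after the alert.

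The cost is a few refits and some wording, with no new data. What remains is the secular trend in care inside the main model, which must be stated, and the choice about ECG, which rests on an assumption that the data cannot test.
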